### **9.2 Populations**

**Intent-to-Treat (ITT) population:** All enrolled subjects who have taken at least one dose of study drug.

**Efficacy Evaluable (EE) population:** All subjects in the ITT population who have analyzable baseline data and 12 weeks of hot flash data. Subjects must also be at least 80% compliant with taking study drug with no major protocol deviations, including no major inclusion/exclusion deviations.

**Efficacy Evaluable Interim Analysis (EEIA) population:** All subjects in the ITT population who have analyzable baseline data and 6 weeks of hot flash data. Subjects must also be at least 80% compliant with taking study drug with no major protocol deviations, including no major inclusion/exclusion deviations.

**Safety population:** All subjects that receive at least one dose of study medication. The safety analyses will be conducted on this population.

### **9.3 Efficacy Analyses**

The primary efficacy analyses will be among the EE (EEIA) population. The comparison of percentage change in frequency from baseline to Week 6 between the placebo arm and each

of the 10 mg and 50 mg dose arms will be of primary interest in Stage 1. In Stage 2, the comparison of percentage change in frequency from baseline to Week 6 between the placebo arm and the 100 mg dose arm will be of primary interest.

Subjects will record events of hot flashes (frequency and severity) utilizing an application on an electronic device (i.e. smartphone). An example of the specific questions asked and definitions of severity are included in [Appendix C](#)

### **9.3.1 Primary Analyses**

#### **9.3.1.1 Hot Flash Frequency, Week 6 (Day 42)**

Mixed models repeated measures (MMRM) analyses that incorporate, treatment, time, and the treatment\*time interactions will be the primary analytical method for the percentage change in the frequency of moderate to severe hot flashes. The percentage change from baseline in frequency of moderate to severe hot flashes in each active arm will be compared to the placebo arm at Week 6 (Day 42). The analysis will be handled in two ways within the MMRM framework: (1) the means analysis comparing the change from baseline to Week 6, and (2) the slope analysis comparing the rate of change from baseline to Week 6.

The primary endpoint in the study will be analyzed when the last patient reaches Day 42. However, the clinical site and patients will remain blinded through the completion of the Day 84 efficacy assessments and the follow up safety visits.

Each subject's hot flash frequency will be summed on a weekly basis. Because the MMRM is the primary analytical method, it will be possible to estimate Week 6 changes from baseline by incorporating the preceding weeks' data, e.g., Week 6 estimates will incorporate data from baseline and Week 1 through Week 6. Analyses will be performed for the EE (EEIA) populations.

If the MMRM model does not converge or has poor fit, T-tests or non-parametric tests, if the data are deemed non-normally distributed, will compare changes over time within (Paired T-test or Wilcoxon sign-rank test) an arm and between (T-test or Wilcoxon rank sum test) each active arm and the placebo arm, respectively.

The Hochberg procedure (Hochberg Y, 1988) will be applied to control for the multiple comparisons associated with the comparisons between the two dose arms and placebo and the two different MMRM analyses (means, slope) in the primary analyses of frequency of hot flashes in Stage 1. The analyses for Stage 2 will be treated similarly to address the multiplicity of the MMRM analyses. Note that the placebo arm in Stage 2 comprises a cohort of subjects distinct from those placebo subjects that were enrolled during Stage 1.

### **9.3.2 Secondary Analyses**

#### **9.3.2.1 Hot Flash Frequency (Weeks 4, 8, 10 and 12) and Severity (Weeks 4, 6, 8, 10, and 12)**

Mixed models repeated measures (MMRM) analyses that incorporate, treatment, time, and treatment\*time interactions will be the primary analytical method for the percentage change in both the frequency and severity of moderate to severe hot flashes: frequency (severity). The percentage change from baseline in frequency (severity) of moderate to severe hot flashes in each active arm will be compared to the placebo arm at Week 4 (Day 28), Week 8 (Day 56), Week 10 (Day 70), and Week 12 (Day 84). Each analysis will be handled in two ways within the MMRM framework, as described for the primary analysis above.

Each subject's hot flash frequency (severity) will be summed on a weekly basis. Because the MMRM is the primary analytical method, it will be possible to estimate Weeks 4, 8, 10, and 12 changes from baseline by incorporating the preceding weeks' data, e.g., Weeks 4, 8, 10, and 12 estimates will incorporate data from baseline and Week 1 through Weeks 4, 8, 10, and 12. Analyses will be performed for the ITT and PP populations.

If the MMRM model does not converge or has poor fit, T-tests or non-parametric tests, if the data are deemed non-normally distributed, will compare changes over time within (Paired T-test or Wilcoxon sign-rank test) an arm and between (T-test or Wilcoxon rank sum test) each active arm and the placebo arm, respectively.

If the MMRM model does not converge or has poor fit, non-parametric tests will compare changes over time within (Wilcoxon sign-rank test) an arm and between (Wilcoxon rank sum test) active arms and the placebo arm, respectively.

The Hochberg procedure (Hochberg Y, 1988) will be applied to control for the multiple comparisons associated with the comparisons between the two dose arms and placebo and the two different MMRM analyses in the analyses of frequency (severity) of hot flashes for Stage 1. The analyses for Stage 2 will be treated similarly to address the multiplicity of the two MMRM analyses. Note that the placebo arm in Stage 2 comprises a cohort of subjects distinct from those placebo subjects that were enrolled during Stage 1.

The severity of hot flash analysis will be the average severity at baseline of only the moderate and severe hot flashes. The severity of hot flashes analysis at Weeks 4, 6, 8, 10, and 12 will be the average severity of all hot flashes, i.e. mild, moderate, and severe hot flashes.

See the Statistical Analysis Plan for the study for full and complete statistical analyses planned for the study.

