## 6.3 Efficacy Analyses

## 6.3.1 Analyses of all hot flash frequency and severity endpoints both Primary and Secondary

The following conventions apply to all analyses of hot flash frequency and severity data:

Population: The EE population (efficacy evaluable) population will be the population of interest in the primary and all secondary endpoint analyses. The EEIA (efficacy evaluable interim analysis) population will be the population of interest for the analysis conducted at Week 6. The ITT population will be used in the sensitivity analyses to verify that the findings remain consistent.

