#### 6.9 Changes to Methods Planned in the Protocol

At the time the SAP was finalized, there were no changes to methods planned in the protocol. Any other changes from the SAP, including any ad-hoc analysis, will be detailed in the clinical study report.

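### Protocol and SAP name different analysis sets for the nine hot flash secondary endpoints, and the SAP's lead set makes early endpoints conditional on 12 weeks of diary data

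*Protocol*

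**What the plan says.** Protocol 9.3.2.1 covers the secondary frequency and severity endpoints and gives their analysis sets in one sentence: "Analyses will be performed for the ITT and PP populations". It ranks neither set above the other.

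Protocol 9.2 defines four sets: ITT, EE, EEIA and Safety. ITT is "All enrolled subjects who have taken at least one dose of study drug". EE is "All subjects in the ITT population who have analyzable baseline data and 12 weeks of hot flash data", with the further conditions of 80% drug compliance and no major deviations. EEIA is the same with 6 weeks of diary data in place of 12. For the primary endpoint, Protocol 9.3 states: "The primary efficacy analyses will be among the EE (EEIA) population".

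SAP 5 defines the same four sets. SAP 6.3.1, whose conventions cover all hot flash analyses, says that EE "will be the population of interest in the primary and all secondary endpoint analyses". It then assigns EEIA to the analysis conducted at Week 6 and gives ITT a sensitivity role. SAP 6.9 states: "At the time the SAP was finalized, there were no changes to methods planned in the protocol".

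SAP 6.7, on the interim analysis of Week 6 frequency and severity, first places the summaries and the MMRM in both ITT and EEIA. It later says that every interim analysis is done in EEIA.

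**The concern.** Three things do not fit together. The protocol relies on a set, PP, that has no definition. The two documents give ITT a different standing for the same endpoints: listed on equal terms in the protocol, sensitivity only in the SAP. And the SAP section meant to disclose such differences reports none.

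The choice also has a statistical consequence. EE admits only men "who have analyzable baseline data and 12 weeks of hot flash data". If EE leads, whether a man counts in the Week 4 result depends on what he does in Weeks 5 to 12. An early comparison is then made among later completers, and the protection of randomisation is weakened if completion differs by arm. The protocol gives reasons why completion might not be random. Section 8.11 takes men off treatment for drug-related toxicity or liver enzyme rises. Section 8.16 withdraws men who need a disallowed medication, and several medications on the prohibited list in 8.15 are ones that the introduction describes as hot flash treatments. This is a plausible mechanism. The documents do not show that it operates.

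**Working it through.** The check is mainly a comparison of text.

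**1. Endpoints affected.** The title of Protocol 9.3.2.1 lists frequency at Weeks 4, 8, 10 and 12 (4 endpoints) and severity at Weeks 4, 6, 8, 10 and 12 (5 endpoints): 4 + 5 = 9. These are items 1 to 9 of the secondary list in Protocol 5.3.2 and of the ordered list in SAP 6.3.1.

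**2. Sets side by side.**

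| Analysis | Protocol | SAP |
|---|---|---|
| Primary (frequency, Week 6) | EE (EEIA) | EE; EEIA for the analysis at Week 6 |
| Nine hot flash secondaries | ITT and PP, no lead | EE leads; EEIA for the analysis at Week 6; ITT sensitivity |
| Bone markers | ITT | ITT |

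The primary endpoint and the bone markers agree. The conflict is confined to the nine.

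**3. Is PP defined anywhere?** It is not in Protocol 9.2, SAP 5 or either abbreviation list. EE's compliance and deviation conditions resemble a per-protocol set, so PP may be a leftover name for EE, but neither document says so. Even if it is, the role of ITT still differs between the documents.

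**4. The interim statements.** SAP 6.7 names ITT and EEIA for Week 6 frequency and severity, then EEIA alone for everything. It also says that the associated sensitivity analyses are not run at the interim, although ITT is a sensitivity set under SAP 6.3.1. Week 6 severity, the first secondary endpoint in the SAP's order, is therefore unsettled within the SAP itself.

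**5. What the 12-week condition does.** Sort the nine endpoints by whether EE demands diary data beyond the endpoint week:

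- Weeks 4, 8 and 10, frequency and severity: 3 × 2 = 6 endpoints. Data are required for a further 8, 4 and 2 weeks respectively (12 − 4, 12 − 8, 12 − 10).
- Week 12, frequency and severity: 2 endpoints. No later data are required.
- Week 6 severity: 1 endpoint. At the interim it is analysed in EEIA, which stops at Week 6, so there is no selection on later weeks.

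Total 6 + 2 + 1 = 9. A man who records fully through Week 8 and then stops is outside EE. He is lost from the lead analysis of four endpoints (Weeks 4 and 8, frequency and severity) for which his data are complete.

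**6. Does the model need the later weeks?** No. Protocol 9.3.2.1 builds each estimate from baseline and the weeks up to the endpoint week. The SAP code does the same, restricting the data to weeks at or before the target week. The Week 4 model therefore uses nothing after Week 4, and an MMRM can include men with incomplete series. The 12-week condition brings no data into the early models. It only removes men.

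**7. Size.** Neither document gives a rate of discontinuation or of exclusion from EE, so no loss of precision is calculated.

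**The case against.** The best defence is that the SAP is clear where it matters. Protocol 9.3.2.1 ends by sending the reader to the SAP for the complete analyses, and SAP 6.3.1 names a lead set. Both documents also plan ITT plus a restricted set, so the remaining disagreement could be called one of order. Part of this stands: the pointer softens the conflict. It does not say that the SAP overrides the protocol, though, and the SAP denies that anything differs.

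The documents do not support several stronger readings that a reader might infer:

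- *That the fixed-order testing turns on which document is read.* The ordering appears only in the SAP, which names its own lead set. Protocol 9.3.2.1 has the Hochberg procedure but no ordering. Anyone applying the order is already working from the SAP.
- *That the SAP analyses all nine endpoints in EE.* EEIA applies to the analysis at Week 6, so the 12-week selection does not reach Week 6 severity at the interim.
- *That EE costs a definite amount of precision against 30 men per arm in ITT.* That needs an exclusion rate the documents do not give. It would also treat men who stop early as fully informative in ITT. Their diary ends at early termination (SAP 4.8) and SAP 6.1.2 does not impute missing weeks, so ITT would not hold 30 observed men per arm at Weeks 10 and 12 either.

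It is also fair to say that selection on 12-week data is a criticism of EE that would stand even if the documents agreed. It belongs here because it bears on which way to reconcile them.

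**Conclusion.** The point holds. For nine secondary endpoints the protocol names ITT and an undefined set with no lead, the SAP names EE (EEIA at Week 6) with ITT as sensitivity, and SAP 6.9 wrongly reports no change. SAP 6.7 adds an internal contradiction about the interim sets. Under the SAP's lead set, six of the nine endpoints are conditioned on diary completion after the endpoint week.

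The conclusion rests on reading the EE definition literally, as requiring diary data through Week 12. No size is claimed for bias or lost precision, because there is no attrition rate to work from. The primary endpoint and the bone markers are not affected. For secondary endpoints in a Phase 2 trial this is something to correct. It does not undermine the primary analysis.

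**What to change.** Name one lead set for the nine endpoints, in the same words, in Protocol 9.3.2.1 and SAP 6.3.1. ITT is preferable: it is defined in both documents, the protocol already names it for these endpoints, and the planned MMRM can use all available weeks up to the endpoint week. EE and EEIA would then be supportive. Delete PP, reconcile the two interim statements in SAP 6.7, and record the change in SAP 6.9. Settle this before the unblinded Week 6 results are seen.

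The edits are short, but changing a pre-specified lead set is more than editorial. Non-adherence may dilute the ITT estimates slightly. The primary endpoint would stay on EE/EEIA, so the lead set would change between the primary and the first secondary endpoint, and both documents should say so.

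If the sponsor prefers a restricted lead set, it should align Protocol 9.3.2.1 with the SAP, require diary data only through the endpoint week instead of all 12 weeks, and still disclose the change in SAP 6.9. That keeps one kind of population throughout the ordered testing and removes the selection on later weeks. The exclusions for drug compliance and major deviations would remain.

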### **9.3.2.2 Bone Turnover Markers**

Values at baseline and each scheduled assessment (Day 84) for each treatment group will be assessed. The mean, standard deviation, median, minimum, and maximum values will be summarized at each of these time points. The percentage change from baseline to Day 84 will be summarized as well. This will be done for the ITT population. T-tests or non-parametric tests, if the data are deemed non-normally distributed, will compare changes over time within (Paired T-test or Wilcoxon sign-rank test) an arm and between (T-test or Wilcoxon rank sum test) each active arm and the placebo arm, respectively.

## **9.3.3 Exploratory Analyses**

### **9.3.3.1 Serum PSA**

Values at baseline and each scheduled assessment (Days 30, 60, and 84) in each treatment group will be assessed. The mean, standard deviation, median, minimum, and maximum levels will be summarized at each of these time points. The percentage change from baseline to each time point will be summarized as well. This will be done for the ITT population. T-tests or non-parametric tests, if the data are deemed non-normally distributed, will compare changes over time within (Paired T-test or Wilcoxon sign-rank test) an arm and between (T-test or Wilcoxon rank sum test) each active arm and the placebo arm, respectively.

### **9.3.3.2 Change in Serum Total and Free Testosterone Concentration**

Values at baseline and each scheduled assessment (Days 30, 60, and 84) for each treatment group will be assessed. The mean, standard deviation, median, minimum, and maximum lab values will be summarized at each of these time points. The percentage change from baseline to each time point will be summarized as well. This will be done for the ITT population. T-tests or non-parametric tests, if the data are deemed non-normally distributed, will compare changes over time within (Paired T-test or Wilcoxon sign-rank test) an arm and between (T-test or Wilcoxon rank sum test) each active arm and the placebo arm, respectively.

### **9.3.3.3 Serum SHBG**

Values at baseline and each scheduled assessment (Days 30, 60, and 84) for each treatment group will be assessed. The mean, standard deviation, median, minimum, and maximum lab values will be summarized at each of these time points. The percentage change from baseline to each time point will be summarized as well. This will be done for the ITT population. T-tests or non-parametric tests, if the data are deemed non-normally distributed, will compare changes over time within (Paired T-test or Wilcoxon sign-rank test) an arm and between (T-test or Wilcoxon rank sum test) each active arm and the placebo arm, respectively.

### **9.3.3.4 Pharmacokinetic Assessments**

VERU-944 trough concentrations will be determined in each subject and used to calculate the mean, median, standard deviation, coefficient of variation, maxima and minima within each arm of the trough levels of VERU-944.

### **9.3.4 Safety Analysis**

The frequency of adverse events (AEs) will be tabulated by MedDRA term and system organ class. The incidence of AEs and the maximum intensity and frequency of AEs will be summarized. A new onset AE is defined as an AE that was not present prior to treatment with study medication but appeared following treatment, or was present at treatment initiation but worsened during treatment. An AE that was present at treatment initiation but resolved and then reappeared while the patient was on treatment is a new-onset AE (regardless of the intensity of the AE when the treatment was initiated).

All laboratory results, vital sign measurements, and other safety variables will be summarized using appropriate descriptive statistics. Changes from baseline will be computed and will be summarized using appropriate descriptive statistics.

#### **9.3.4.1 Data Safety Monitoring Board**

There will be no formal Data Monitoring Committee for this study. Safety data, including all SAEs, will be reviewed on an ongoing basis by a Safety Review Team comprised of the Medical Monitor, and representatives of the Sponsor. This Safety Review Team will meet at least monthly. Additional ad hoc meetings will be scheduled if required to evaluate the safety and/or thromboembolic events further.

## **10.0 ADMINISTRATION PROCEDURES**

### **10.1 Study Conduct and Compliance**

The study will be conducted in accordance with the Code of Federal Regulations (21 CFR parts 50, 54, 56, 312, and 314), which originates from the ethical principles laid down in the Declaration of Helsinki. Good Clinical Practices (GCPs) and the policies and procedures of the Sponsor and/or its authorized representative will also be followed. This clinical trial will be overseen and managed by a contract research organization (CRO) and the Sponsor. The CRO will be responsible for data management, data handling, statistical analysis, quality assurance and the final study report. The Sponsor will be responsible for project management of the CRO and clinical monitoring.

## **10.2 Informed Consent**

Prior to study entry, the Investigator, or a person designated by the Investigator, will explain the nature, purpose, benefits and risks of participation in the study to each subject, subject's legally acceptable representative or impartial witness. Written informed consent must be obtained prior to the subject entering the study (before initiation of any study-related procedure and administration of the investigational medicinal product (IMP)). Sufficient time will be allowed to discuss any questions raised by the subject.

The Sponsor will provide a sample informed consent form. The final version controlled form must be agreed to by the Sponsor and the IEC/IRB and must contain all elements included in the sample form, in language readily understood by the subject. Each subject's original consent form, personally signed and dated by the subject or by the subject's legally acceptable representative, and by the person who conducted the informed consent discussion, will be retained by the Investigator. The Investigator will supply all enrolled subjects with a copy of their signed informed consent.

The consent form may need to be revised during the trial should important new information become available that may be relevant to the safety of the subject or as a result of protocol amendments. In this instance approval should always be given by the IEC/IRB. It is the Investigator's responsibility to ensure that all subjects subsequently entered into the study and those currently in the study sign the amended form. This is documented in the same way as previously described. Subjects who have completed the study should be informed of any new information that may impact on their welfare/wellbeing.

The Investigator should, with the consent of the subject, inform the subject's primary physician about their participation in the clinical trial.

## **10.3 Protocol Amendments**

In the event that an amendment to this protocol is required, it will be classified into one of the following three categories:

- **Non-Substantial Amendments** are those that are not considered ‘substantial’ (e.g., administrative changes) and as such only need to be notified to the IECs/IRBs or Competent Authorities (CA) for information purposes.
- **Substantial Amendments** are those considered ‘substantial’ to the conduct of the clinical trial where they are likely to have a significant impact on:
  - the safety or physical or mental integrity of the subjects;
  - the scientific value of the trial;
  - the conduct or management of the trial; or
  - the quality or safety of the IMP used in the trial.

Substantial amendments must be notified to the IECs/IRBs and CA. Prior to implementation, documented approval must be received from the IECs/IRBs. In the case of the CA in the EU member states, approval or ‘favorable opinion’ can be assumed if the CA has raised no grounds for non-acceptance during an allocated time period (to be confirmed with the Sponsor’s Regulatory Affairs (RA) representative) following acknowledgment of receipt of a valid application to make a substantial amendment.

- **Urgent Amendments** are those that require urgent safety measures to protect the trial subjects from immediate hazard and as such may be implemented immediately by the Sponsor with subsequent IECs/IRBs and CA notification, forthwith.

